8.3.2 AE Severity/Intensity

The severity (intensity) grades that will be used for this study are defined in the DAIDS AE Grading Table Version 1.0, Dec 2004 and Addendum 1 to the table. These tables are available at: <http://rcc.tech-res.com/eae.htm>.

8.3.3 Serious Adverse Event

Serious Adverse Event (SAE) will be defined per 21 CFR 312.32 guidelines. A serious adverse event is any adverse experience occurring at any dose that results in any of the following outcomes:

- Death
- A life-threatening adverse event
- Inpatient hospitalization or prolongation of existing hospitalization
- A persistent or significant disability/incapacity, or
- A congenital anomaly/birth defect.

Important medical events that may not result in death, be life-threatening, or require hospitalization may be considered a serious adverse event when, based upon appropriate medical judgment, they may jeopardize the patient or participant and may require medical or surgical intervention to prevent one of the outcomes listed in this definition. Examples of such medical events include allergic bronchospasm requiring intensive treatment in an emergency room or at home, blood dyscrasias or convulsions that do not result in inpatient hospitalization, or the development of drug dependency or drug abuse.

Study sites will report any SAEs to Starpharma within 24 hours of their knowledge of the SAE. SAEs will be reported to the FDA by Starpharma Pty Ltd. SAE reports sent to the FDA will be simultaneously sent by Starpharma Pty Ltd to the DAIDS and NICHD Medical Officers.

8.3.4 Adverse Event Relationship to Study Product

Relatedness is an assessment made by a study clinician of whether or not the event is related to the study agent. Degrees of relatedness will be categorized as one of the following.

Definitely related: adverse event and administration of study agent are related in time, and a direct association can be demonstrated with the study agent.

Probably related: adverse event and administration of study agent are reasonably related in time, and the adverse event is more likely explained by the study agent than by other causes.

Possibly related: adverse event and administration of study agent are reasonably related in time, and the adverse event can be explained equally well by causes other than the study agent.

Probably not related: a potential relationship between administration of study agent and adverse event could exist, but is unlikely, and the adverse event is most likely explained by causes other than the study agent.

Not related: the adverse event is clearly explained by another cause unrelated to administration of the study agent. Reportable events must have documentation to support the determination of “not related”.

8.4 Expedited Adverse Event Reporting Requirements

This section outlines Expedited Adverse Event (EAE) reporting requirements for MTN-004. Study sites will receive training on EAE reporting prior to the onset of study enrollment.

8.4.1 Expedited Adverse Event Reporting to DAIDS and Starpharma Pty Ltd

The EAE reporting requirements and definitions for this study and the methods for expedited reporting of AEs to the DAIDS RCC Safety Office are defined in “The Manual for Expedited Reporting of Adverse Events to DAIDS” (DAIDS EAE Manual) **dated May 6, 2004**. The DAIDS EAE Manual is available on the RCC website: <http://rcc.tech-res-intl.com/>. The DAIDS EAE Manual is also available in the MTN-004 Study Operations Manual.

AEs reported on an expedited basis must be documented on the DAIDS Expedited Adverse Event Reporting Form (EAE Reporting Form) available on the RCC website: <http://rcc.tech-res-intl.com/>.

EAEs must be faxed to DAIDS and Starpharma Pty Ltd as outlined in the SSP. Medical Officers from both DAIDS and NICHD are also to receive timely and synchronous communications of any adverse event reported to the RCC from the sites. They will engage in any necessary dialogue or consultation with each other in order to render a decision. If agreement cannot be reached, the ultimate decision will be rendered by the Medical Officer from the MTN’s primary sponsoring institute (NIAID/DAIDS) (or the individual designated to cover for them in their absence).

8.4.2 EAE Reporting Requirements for this Study

EAE Reporting Level

This study uses the **Intensive Level** of expedited AE reporting as defined in the DAIDS EAE Manual.

Study Agents for Expedited Reporting to DAIDS

The study agents that must be considered in determining relationships of AEs requiring expedited reporting to DAIDS are: study agent delivery applicator, VivaGel[®], VivaGel[®] placebo, and HEC gel.

Study Agents for Expedited Reporting to Starpharma Pty Ltd

The study agents that must be considered in determining relationships of AEs requiring expedited reporting to Starpharma Pty Ltd are: study agent delivery applicator, VivaGel[®], VivaGel[®] placebo, and HEC gel.

Grading Severity of Events

The DAIDS AE Grading Table, Addendum 1 (Female Genital Grading Table for Use in Microbicide Studies) will be the primary tool for grading adverse events for this protocol, with the exception of asymptomatic bacterial vaginosis and asymptomatic candidiasis which will not be a reportable AE as noted above. AEs not included in that table will be graded by the DAIDS AE Grading Table Version 1.0, Dec 2004. In cases where an AE is covered in both tables, the Female Genital Grading Table for Use in Microbicide Studies will be the grading scale utilized. These tables are available at: <http://rcc.tech-res.com/eae.htm>.

The Division of AIDS Table for Grading the Severity of Adult and Pediatric Adverse Events (DAIDS AE Grading Table), Version 1.0, December, 2004 is available on the RCC website at <http://rcc.tech-res.com/eae.htm>. The DAIDS AE Grading Table is also available in the MTN-004 Study Specific Procedures (SSP) Manual.

EAE Reporting Periods

AEs must be reported on an expedited basis at the **Intensive Level** during the Protocol-defined EAE Reporting Period, which is:

The entire study duration for an individual participant (from study enrollment until study completion or discontinuation of the participant from study participation for any reason).

After the end of the Protocol-defined EAE Reporting Period stated above, sites must report serious, unexpected, clinical suspected adverse drug reactions if the study site staff becomes aware of the event on a passive basis, i.e., from publicly available information.

8.5 Local Regulatory Requirements

Site investigators will submit AE information in accordance with local regulatory agencies' or other local authorities' requirements. This reporting will include site IRB-mandated reporting of AEs, SAEs, and other relevant safety information.

9 CLINICAL MANAGEMENT

This section summarizes guidelines for clinical management for individual participants in the case of unplanned health events, including product toxicity, other disease events, and pregnancy.

9.1 Toxicity Management

Based on results from the first Phase 1 study of VivaGel[®], toxicity in study participants is not expected in this trial. In response to AEs reported by study participants and/or observed upon exam by study staff, the study site principal investigator or designee will recommend either continuation or withholding study gel use consistent with the criteria in Appendix II.

Study gel use also will be withheld or discontinued in the event of an Expedited Adverse Event (EAE) that is judged by the site principal investigator or designee to be definitely, probably, possibly, or probably not related to the study gel or applicator. Unless the participant withdraws her consent, she will remain in the study to complete the safety

evaluations (unless clinically contraindicated) according to Appendix I, and/or as specified in Appendix II.

9.2 Other Disease Events

Management of confirmed sexually transmitted infections/sexually transmitted diseases, commonly referred to as STIs or STDs, and other forms of vaginitis and cervicitis will be in accordance with CDC Guidelines.

9.3 Pregnancy

All participants will be instructed to report pregnancies to site investigator or to the study staff who will in turn report to the site investigator; the site investigator will inform PSRT. The site investigator will counsel the participant and discuss possible risks if the pregnancy is continued according to site-specific SOPs.

Participants who are found to be pregnant during the study period will continue to be followed for safety reasons until the end of their study participation (study exit visit). Participants who are pregnant at the time of the study exit visit will continue to be followed until the pregnancy outcome is ascertained or it is determined that, after multiple attempts, pregnancy outcome cannot be ascertained. The site PIs will attempt to ascertain the pregnancy outcome, and pregnancy outcomes will be reported to SCHARP on the Pregnancy Outcome form. Any pregnancies will be reported to the PSRT. Pregnancies with abnormal outcomes will be reported according to all applicable EAE guidelines listed in Section 8.4.

Sites will provide a single brand of lubricated (non-N-9 or -spermicide containing), male, latex condoms for the purpose of this study, and facilitate participants' access to all contraceptive methods. In the event of pregnancy, sites will counsel participants and will facilitate access to services, according to the site-specific SOPs. However, sites will not be responsible for paying for pregnancy-related care. Participants who become pregnant during the course of the study will discontinue study gel use while they are pregnant, but will not routinely be withdrawn from the study. Rather, if the participant does not withdraw her consent, every effort will be made to complete the safety evaluations according to Appendix I.

For participants who become pregnant, all protocol-specified procedures will continue except:

- Administration of study gel (The site staff will make every effort to recover any unused study product once pregnancy is diagnosed.)

9.4 Criteria for Discontinuation of Study Product, and Discontinuation of Study Participation

Participants may voluntarily withdraw from the study for any reason at any time. The principal investigators may withdraw participants to protect their safety, and/or if participants are unable or unwilling to comply with study procedures. The investigators may withdraw a participant from the study if any condition in the opinion of the investigator would impose a health risk to the participant or interfere with the evaluation of the study product. Participants withdrawn for safety reasons by the investigator will continue to be followed with the protocol-determined schedule of follow-up visits, unless consent is withdrawn.

Discontinuation of study participation will occur only if certain conditions below are met. These conditions are related to safety as well as impact on reaching planned study endpoints.

9.4.1 Criteria for Permanent Study Product Discontinuation for an Individual Participant

The criteria for permanent discontinuation of further study product use for an individual participant are:

- Signs or symptoms of STI(s)/RTI(s) requiring treatment according to the judgment of the investigator
- Study product-related toxicity (see Section 9.1)
- Pregnancy or breastfeeding
- Completion of regimen as defined in the protocol
- Request by participant to terminate treatment
- Clinical reasons determined by the physician

The participant will continue to be followed with the participant's permission if study product is discontinued. No subsequent modifications to the visit schedule and duration of continued follow-up will be made, except no study product will be administered.

9.4.2 Criteria for Premature Study Discontinuation for an Individual Participant

Safety or other considerations may make it appropriate to have a participant prematurely discontinue the study. The criteria for premature discontinuation from the study for an individual participant are:

- Lost to follow-up as evidenced by failure by the participant to attend two consecutive clinic visits
- Participant repeatedly non-compliant with study treatment as prescribed (e.g. non-compliant with instructions for dosage, route, regimen, or male condom use)
- Request by participant to withdraw

- Request of the primary care provider if s/he thinks the study is no longer in the best interest of the participant

10 STATISTICAL CONSIDERATIONS

10.1 Overview and General Design

This is a two site, Phase I, double blind, randomized, controlled comparison with 14 days of twice daily exposure to VivaGel[®], VivaGel[®] placebo, or HEC gel, and follow-up among HIV-uninfected sexually active women.

10.2 Study Endpoints

10.2.1 Primary Endpoint

Consistent with the primary study objective to assess the safety of study drug when administered twice daily for 14 consecutive days on vulvar and cervicovaginal mucosa, the following primary endpoints will be assessed:

- Abnormal genital symptoms judged by the Investigator to be possibly, probably, or definitely related to product use;
- Abnormal pelvic exam findings, (excluding findings observed by colposcopy only), judged by the Investigator to be possibly, probably, or definitely related to product use;
- Grade 3 or higher laboratory values (as defined by the DAIDS Toxicity Tables) for hematology, liver function, creatinine level and coagulation judged by the Investigator to be possibly, probably, or definitely related to product use;
- Adverse experiences judged by the Investigator to be possibly, probably, or definitely related to product use.

10.2.2 Secondary Endpoints

Consistent with the secondary study objectives to assess adherence to, and acceptability of, a short-term regimen of VivaGel[®], and to assess the effect of this regimen on vaginal microflora, the following endpoints will be assessed:

- The proportion of participants who report via adherence questionnaire that they were adherent to the product use regimen, with adherence defined as the application of at least 80% of the expected number of doses of study product over the two weeks of product use;

- The proportion of participants who at their Two-Week Clinic Visit report via the acceptability questionnaire that they would be very likely to use the candidate microbicide during sexual intercourse in the future;
- Reported positive and negative aspects of using study product;
- Changes in vaginal flora.

10.2.3 Exploratory Endpoints

- Changes in cervical cytokine, innate immune factor (secretory leukocyte protease inhibitor (SLPI) and lactoferrin) expression, and functional activity (antiviral and antibacterial) in cervicovaginal secretions
- Detection of SPL7013 in blood samples at Day 0 and Two-Week Clinic Visit (Target Day 14)
- To assess the effects of VivaGel[®] on colposcopic findings

Changes within each arm and between arms will be reported.

10.3 Study Hypothesis

MTN-004 hypothesizes that VivaGel[®] will be safe, well-tolerated and acceptable for twice daily vaginal application among healthy sexually active young women.

10.4 Sample Size

The primary aim of the study is to assess the local and systemic safety of vaginal application of VivaGel[®] versus placebo gel among HIV uninfected women. The proposed total sample size is approximately n=61 evaluable participants with approximately 36 included in comparisons between VivaGel[®] and the HEC Gel (18 participants in each of the 2 arms), and approximately 43 included in comparisons between VivaGel[®], and VivaGel[®] placebo (18 participants in each of the 2 arms plus 7 previously enrolled). This sample size is based upon the size of similar Phase 1 studies of topical microbicide products. Additional participants may enroll in the study, at the discretion of the protocol team, to replace currently enrolled participants who are non-adherent to the study product and/or the study visit schedule. Finally, if for some reason a site experiences difficulty reaching its accrual target, consideration will be given to shifting enrollment “slots” to the other site, with prior approval of the Protocol Chair.

As a means to characterize the statistical properties of this study, the following table presents the probability of observing zero, at least one, and two or more safety endpoints among the minimum sample size of 18 women using VivaGel[®] for various “true” event rates:

Table 17: Analysis of Adverse Event Frequency with n = 18

Event Rate	P (0 events n=18)	P (≥ 1 event n=18)	P (≥ 2 events n=18)
1%	0.83	0.17	0.01
5%	0.40	0.60	0.23
10%	0.15	0.85	0.55
15%	0.05	0.95	0.78
25%	<0.01	>0.99	0.96
35%	<0.01	>0.99	>0.99
45%	<0.01	>0.99	>0.99

For example, if the true rate of a given endpoint is five percent, the probability that the endpoint will be observed in at least one of the (minimum of) 18 women exposed to VivaGel[®] is 0.60.

The actual number of women using VivaGel[®] who will be available for analysis is unknown, but is likely to be approximately 21. Given this, the table below presents the probability of observing zero, at least one, and two or more safety endpoints assuming 21 women were randomized to VivaGel[®] for various “true” event rates:

Table 18: Analysis of Adverse Event Frequency with n = 21

Event Rate	P (0 events n=21)	P (≥ 1 event n=21)	P (≥ 2 events n=21)
1%	0.81	0.19	0.02
5%	0.34	0.66	0.28
10%	0.11	0.89	0.64
15%	0.03	0.97	0.84
25%	<0.01	>0.99	0.98
35%	<0.01	>0.99	>0.99
45%	<0.01	>0.99	>0.99

10.5 Randomization Procedures

Women will be randomized at a 1:1:1 ratio to one of the three arms. Randomization will be stratified by site to ensure balanced assignment to each product (VivaGel[®], VivaGel[®] placebo, or HEC gel) within each site. The randomization scheme will be generated and maintained by the SDMC. The SDMC will provide each study site with one set of randomization envelopes to be stored and used in the study clinic. Clinic staff will assign these envelopes in sequential order, by envelope number, to eligible participants. Additional envelopes will be provided to each site for the purpose of enrolling >18 participants per site if non-adherent participants need to be replaced or if enrollment “slots” need to be shifted from one site to another.

Assignment of the randomization envelope is considered the effective act of participant enrollment/randomization. Clinic staff will prepare a written prescription contained within the envelope that, among other things, documents the randomization envelope number and randomization code indicating the product (VivaGel[®], VivaGel[®] placebo, or

HEC gel) to which the participant was assigned. Multiple codes will be utilized to conceal and protect the randomization assignments in this study. Clinic staff will store assigned randomization envelopes and copies of the study prescription in participants' study charts.

10.6 Justification for Placebo Gels

Inclusion of placebo gels in this safety trial will enable investigators to examine the incidence of adverse events in the presence of the study product containing SPL7013 in comparison to those occurring in the presence of the two different placebo gels (one of which is the same formulation as VivaGel[®], but containing no SPL7013, and one of which is a placebo gel that has been used in several placebo controlled microbicide trials) that have been shown to have good safety profiles and low likelihoods of inducing mucosal damage.

10.7 Blinding

Study staff and participants will be blinded to the random assignments of all study participants. All study gels will be supplied in identical, single-use applicators packaged in individual wrappers. Blinding will be maintained until all data are entered into the study database, all study endpoint data and other data included in the final analysis have been cleaned and verified, and the data are ready for final analysis. This will be explained to participants as part of the study.

10.8 Maintenance of Trial Randomization Codes

Trial randomization codes will be maintained by unblinded staff at the SDMC. There are no circumstances under which it is expected that unblinding to blinded study staff or participants will be necessary for the provision of medical treatment or to otherwise protect the safety of study participants.

As described in Section 9.4, in the event that an Investigator is concerned that a participant might be put at an undue risk by continuing product use, the Investigator may discontinue use by this participant; however, knowledge of the specific product to which the participant was assigned should not be necessary to guide further follow up and/or treatment. If an Investigator feels that specific product knowledge is necessary to protect participant safety, the Investigator will notify the PSRT to consider and rule upon the request.

10.9 Participant Accrual and Follow-Up

Based on previous studies of vaginal products with similar eligibility requirements, the accrual of eligible participants with normal reproductive tracts is expected to require the screening of approximately 160 volunteers. The target for retention will be 95% of enrolled participants over the 21-day follow-up period. Therefore, it is anticipated that

approximately 64 women will be enrolled in the study. Accrual is anticipated to take approximately 9 months. Monthly accrual targets will be available in the SSP.

10.10 Data and Safety Monitoring and Analysis

10.10.1 Study Monitoring Committee (SMC)

In addition to the safety monitoring done by the PSRT (described in section 8.1), the MTN SDMC will prepare study progress reports and reports of AEs experienced by study participants (blinded to treatment assignment) for review by the MTN Study Monitoring Committee (SMC). The SMC will conduct interim reviews of study progress (blinded to treatment assignment), including rates of participant accrual, retention, rates of adherence to study gel use, and product safety. These reviews will take place approximately every 90 days, or as needed. At the time of these reviews, or at any other time, the SMC may recommend that the study proceed as designed, proceed with design modifications, or be discontinued.

10.10.2 Data Analysis

For analyses comparing VivaGel[®] to the VivaGel[®] placebo, data from approximately 43 women will be included (18 participants in each of the 2 arms plus 7 previously enrolled) whereas for analyses comparing VivaGel[®] to the HEC gel, data from approximately 36 women will be included (18 participants per arm). All references to “control gel” below apply to 1) the VivaGel[®] placebo in analyses comparing VivaGel[®] to the VivaGel[®] placebo and, 2) the HEC gel in analyses comparing VivaGel[®] to the HEC gel.

When the use of descriptive statistics to assess group characteristics or differences is required, the following methods will be used: for categorical variables, the number and percent in each category; for continuous variables, the mean, median, standard deviation, quartiles and range (minimum, maximum). Within-treatment group assessment of the change from the baseline measurement to a follow-up measurement will be analyzed using McNemar’s test (for categorical response variables) or the paired t-test or Wilcoxon signed-ranks test (for continuous variables). When use of formal testing to assess differences between users of the control gel and users of VivaGel[®] is required, the following methods will be used: for binomial response variables, chi-square tests and logistic regression; for continuous variables, t-tests and linear regression or nonparametric methods if data are non-Normal.

To assess the adequacy of the randomization, control gel and VivaGel[®] participants will be compared for baseline characteristics including demographics, pelvic examination, and laboratory measurements using descriptive statistics. Due to the small sample size, formal comparisons will not be done.

Primary Analyses

The primary aim of the study is to assess the toxicity of VivaGel[®] on vulvar and cervicovaginal mucosa. All visits in which a woman has been exposed to the study product will be included in the primary analysis of safety. Secondary intent to treat analyses may also be performed. To assess safety, the number and the percentages of participants experiencing at least one AE, and the number and percentage experiencing each specific AE will be tabulated by study arm. Each participant will contribute once in each category (i.e. only for highest severity AE for each participant) for the calculation of event rates. The number and percentage of participants experiencing each type of AE (including AEs leading to study discontinuation) will be tabulated by severity and relationship to treatment for each treatment group. AEs that lead to study product discontinuation will be listed in a separate data listing. Overall summaries by treatment group include the number and percentage of participants experiencing: (1) any experience; (2) any moderate, severe, or life-threatening experience. The number and percentage of participants with an AE judged possibly, probably or definitely related to study treatment will be summarized for each treatment group. Grade 3 or higher toxicity for hematology, coagulation function, liver function, or creatinine level is also a primary endpoint. Baseline and Two-Week visit laboratory measures will be summarized and the change in function, defined by the difference between Two-Week and baseline measurements, will be evaluated by treatment group.

Secondary Analyses

One secondary study objective is to assess adherence to a short-term regimen of VivaGel[®]. To assess adherence, the proportion of participants who applied 80% of the expected number of doses of study product over the two weeks of product use will be calculated by treatment arm. All enrolled women will be included in this analysis.

An additional secondary study objective is to evaluate aspects of product acceptability. To evaluate acceptability, the proportion of participants who at their Two-Week Follow-up Visits report via acceptability questionnaire that they would be extremely likely to use the candidate microbicide during sexual intercourse in the future will be calculated by treatment arm. In addition, positive and negative aspects of using the study drug will be listed in order of frequency. All enrolled women with a Two-Week follow-up visit will be included in these analyses.

The final secondary study objective is to assess the effect of a twice-daily short-term regimen of VivaGel[®] on the vaginal microflora of sexually active HIV-uninfected women. To assess the effect of SPL7013 on vaginal flora, clinically significant changes in vaginal flora will be evaluated by the Nugent score with shift tables from baseline (Enrollment) to follow-up visits. The Nugent score is graded 1 to 10 as follows:

1. Normal, 0 to 3
2. Intermediate, 4 to 6

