2.18.4 Rationale for Change in Study Design

MTN-004, Version 2.0 was paused in October 2007 because five of the seven women that had enrolled into the study had experienced some signs and symptoms of genital irritation which were considered to be likely related to their use of the study products. These signs and symptoms were all mild and included vaginal dryness, vulvovaginitis, erythema, pelvic pain, cervical peeling, metrorrhagia, vaginal laceration and vaginal burning sensation, and lasted between 0-16 days (mean 5 days). An interim review of all available data at the time, including laboratory and clinical information, on the seven women who had been enrolled was then conducted. The review was blinded. This assessment confirmed that these signs and symptoms were minor in nature and typical for a Phase I microbicide study. They all resolved completely and rapidly during follow-up. A third study arm is being added and enrollment increased to provide more comprehensive data about the safety of these products that will strengthen the study conclusions. The third study arm will receive HEC gel as an inert placebo to assess the safety and tolerability of VivaGel[®] and the VivaGel[®] placebo, or “vehicle gel.”

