4 STUDY DESIGN

4.1 Identification of Study Design

MTN-004 is a two site, Phase I, double blind, randomized, controlled comparison with 14 days of twice daily exposure to VivaGel®, VivaGel® placebo, or HEC gel, and follow-up among HIV-uninfected sexually active women. Participants in all three arms will receive male condom counseling and free male condoms on an ongoing basis. The study will be conducted at two sites: University of South Florida and University of Puerto Rico.

Table 7: Study Design

Arm	Description	N	Frequency
1	VivaGel® daily use	*18	Twice daily for fourteen consecutive days
2	VivaGel® placebo daily use	*18	Twice daily for fourteen consecutive days
3	HEC gel daily use	18	Twice daily for fourteen consecutive days

*Arms 1 and 2 will each have a final N between 18 and 25.

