4.5 Study Groups

Three study arms including a total of 61 women are planned. Of these 61 women seven were randomized at a 1:1 ratio to VivaGel[®] or VivaGel[®] placebo, and a total of approximately 54 women will be randomized at a 1:1:1 ratio stratified by site to VivaGel[®] VivaGel[®] placebo, or HEC gel, with all three groups applying the product vaginally twice daily (approximately every 12 hours) for 14 days. Additional participants may be enrolled to ensure that a total of approximately 61 evaluable participants complete the three-week study.

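### The rule that keeps the seven Version 2.0 women out of VivaGel–HEC comparisons is not carried into the by-arm safety tables, and the stated tests name neither protocol version nor site

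*Supplement*

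**What the plan says.** - **Two cohorts.** Section 4.5: "Of these 61 women seven were randomized at a 1:1 ratio to VivaGel" or its placebo; about 54 more women are to be allocated across three arms. Section 10.5 for the new cohort: "Women will be randomized at a 1:1:1 ratio to one of the three arms", and "Randomization will be stratified by site to ensure balanced assignment to each product". Letter of Amendment #1 raises the sites from two to three.
- **Why the design changed.** Section 2.18.4 says Version 2.0 was paused because "five of the seven women that had enrolled into the study had experienced some signs and symptoms of genital irritation", judged likely related to product. The HEC arm was added afterwards.
- **Pairwise comparisons.** Section 10.10.2: for VivaGel against vehicle, "data from approximately 43 women will be included (18 participants in each of the 2 arms plus 7 previously enrolled"; for VivaGel against HEC, "data from approximately 36 women will be included (18 participants per arm". Section 10.4 gives the same counts.
- **Primary safety output.** Under Primary Analyses, every visit at which a woman has been exposed counts, and "the number and percentage experiencing each specific AE will be tabulated by study arm". The adherence proportions, also by arm, take all enrolled women.
- **Arm sizes.** The footnote to Table 7 says "Arms 1 and 2 will each have a final N between 18 and 25", against 18 for HEC. Section 10.4 expects about 21 VivaGel women in the analysis.
- **Tests.** For binary outcomes, Section 10.10.2 names chi-square tests and logistic regression, with no stratum or covariate.

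**The concern.** The plan recognises that the seven women are not concurrent with HEC, because it leaves them out of the VivaGel–HEC comparison. The output it describes in most detail, however, is a set of by-arm safety tables, and these are defined by exposure with no mention of version. Read as written, they place the seven in the VivaGel and vehicle columns while the HEC column can hold none.

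The seven are not a neutral addition. Their events are of the same kind as the primary endpoints (related genital symptoms and pelvic findings), and the study was paused because those events were frequent. A cohort halted because its event count was high tends to overstate its own rate. At stake is the reading of the table for which the HEC arm was added: whether VivaGel and its vehicle irritate more than an inert gel.

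A smaller matter is that site is a randomisation stratum and version separates the two cohorts, yet neither enters the stated tests. The two also overlap: the third site joined in 2009, after the October 2007 pause, so none of the seven can come from it.

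**Working it through.** **Plan's own figures.** 18 + 18 + 7 = 43; 18 + 18 = 36; 3 × 18 + 7 = 61. Tables 17 and 18 at a 5% event rate: 1 − 0.95^18 = 0.603 and 1 − 0.95^21 = 0.659, matching the stated 0.60 and 0.66. Table 18's n = 21 requires three Version 2.0 women among the VivaGel users. All these figures reproduce.

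**Inputs**
- Version 2.0 rate: 5/7 = 71.4%, exact 95% CI 29.0% to 96.3% (Section 2.18.4).
- Background rate p under Version 3.0, taken as equal in all arms: 14.3% (HEC gel in an earlier study, 2 of 14 women, Section 2.17); 47% (VivaGel placebo in SPL7013-004, Section 2.11.3); 30% as an assumed middle value. The two sourced rates come from differently defined outcomes and serve only as a range.
- k: number of Version 2.0 women in the VivaGel arm. The actual split is not given.

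**VivaGel column beside HEC.** The pooled VivaGel rate is (18p + k × 5/7)/(18 + k), so the apparent excess over HEC is k(5/7 − p)/(18 + k). Example: k = 4, p = 0.143 gives 4 × 0.571/22 = 0.104.

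| Background p | k = 3 (n = 21) | k = 4 (n = 22) | k = 7 (n = 25) |
|---|---|---|---|
| 14.3% | 8.2 points | 10.4 | 16.0 |
| 30% | 5.9 | 7.5 | 11.6 |
| 47% | 3.5 | 4.4 | 6.8 |

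Limited to Version 3.0 women (18 against 18), the excess is zero by construction.

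If someone tested the unrestricted counts at k = 4 (chi-square without continuity correction, two-sided 0.05, an assumed level because the plan states none), the chance that VivaGel appears significantly worse than HEC with no Version 3.0 difference would move from 2.3% to 10.4% at p = 14.3%, from 2.5% to 6.4% at 30%, and from 3.2% to 4.6% at 47%. The plan does not call for that test; its HEC comparison uses 36 women.

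**VivaGel against vehicle.** The artefact is (18p + k × 5/7)/(18 + k) − (18p + (7 − k) × 5/7)/(25 − k).

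| Background p | 4:3 | 5:2 | 7:0 |
|---|---|---|---|
| 14.3% | 2.2 points | 6.7 | 16.0 |
| 30% | 1.6 | 4.9 | 11.6 |
| 47% | 1.0 | 2.9 | 6.8 |

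The sign reverses with the split, and the mean over 1:1 allocation is zero. Under simple randomisation (an assumption; the scheme is not given) a 4:3 split in either direction has probability 70/128 = 55%, 5:2 has 42/128 = 33%, and 7:0 has 2/128 = 1.6%. At 4:3 the total rejection rate is 2.5%, 4.6% and 6.2% for the three backgrounds, so pooling causes no material inflation.

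Both tables spread the five events evenly over the seven women. Their division between arms is not given, so realised differences could be smaller or larger.

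**The case against.** - **The HEC comparison is already protected.** A reader might infer that the plan compares VivaGel with HEC using the seven women. It does not: both Section 10.4 and Section 10.10.2 set that comparison at about 36. This stands. What remains is the by-arm tables, where no restriction is stated and the arm sizes and exposure rule point to inclusion.
- **VivaGel against vehicle is randomised throughout.** A reader might infer that pooling confounds this contrast. It does not, because allocation between the two gels is 1:1 in both versions. Only chance imbalance is left, and the expectation of about 21 VivaGel women points to a near-even split. This stands.
- **An excess over HEC may be real.** A reader might call it false. The documents do not support that. All seven women used VivaGel or its vehicle, the events were judged likely related, and the 29% to 96% interval covers the 47% seen with this vehicle before. Section 2.18.4 describes no change of product or population that would create a period effect. This stands, but it is also a reason to show the cohorts apart, because the merged column cannot discriminate.
- **Site is minor.** Randomisation is stratified by site; only the analysis ignores it. An unadjusted test after stratified allocation usually errs towards caution, so no false signal follows. Logistic regression could carry the terms, and three sites leave about 18/3 = 6 women per arm per site. This largely stands.
- **No separate SAP is shown.** Covariates and table columns are often settled there, so their absence alone would carry little weight. But Section 10.10.2 does set analysis populations, and its rule for tables diverges from its rule for comparisons.

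**Conclusion.** The point holds as a gap between two rules in Section 10.10.2 and should be mended before unblinding. As written, the main safety tables would set about 21 to 22 women per gel, including a non-concurrent cohort with 5/7 irritation, beside 18 concurrent HEC women. The apparent VivaGel excess over HEC would be about 4 to 10 points with three or four such women. That size is conditional: it assumes that the 71% is a period or selection effect, that the Version 3.0 rate is the same in all arms and lies between 14% and 47%, and that the five events are spread evenly. If the gels themselves irritate, some or all of the excess is genuine.

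For VivaGel against vehicle the consequence is small: about 1 to 2 points in either direction at a 4:3 split, and more only at rarer splits. Leaving site out of the tests is a mismatch with the randomisation whose size the documents do not allow one to state.

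**What to change.** In Section 10.10.2:
1. State that any table or contrast with an HEC column is limited to women randomised under Version 3.0, and show the seven Version 2.0 women in a separate column.
2. Where formal between-arm tests are done, stratify by site, and for VivaGel against vehicle also by protocol version, using Mantel-Haenszel or exact stratified methods.
3. Add a Version-3.0-only VivaGel against vehicle result as a sensitivity analysis.

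The cost is a few sentences and one table column. No data are dropped and no study procedure changes. The downside is sparse strata, which Mantel-Haenszel and exact methods are suited to handle.
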